## 5. Study design

## 5.1 Design

In this study, we propose to leverage a pre-planned departmental initiative of default prescriptions to reduce unnecessary daily x-ray imaging in palliative radiation treatments.

This study follows a pragmatic stepped wedge design with two comparison groups: (1) a usual practice group (control group) and (2) a default radiation treatment prescription group (intervention group), in which the usual practice group will subsequently rollover from control to intervention. One group is comprised of physicians who practice at the Perelman Center for Advanced Medicine (PCAM). Another group is comprised of non-PCAM physicians at our network satellites (Pennsylvania Hospital, Chestnut Hill Hospital, Doylestown Hospital, and Valley Forge). As is standard practice for implementation of QI initiatives in our department, we will implement the intervention at one network site prior to implementing the intervention at all

[figure not shown]
sites. These groups will be assigned to the intervention or usual care at the start of the study by coin flip. Subsequently, the usual practice group will rollover into the default intervention.

Intervention. The default intervention will be started in February 2017. It will be comprised of default prescription order sets that do not include daily imaging for brain/ CNS, bone, and soft tissue metastases (See Figure 1). The defaults will be immediately preceded by a department wide session with intervention group physicians and therapy staff announcing the initiation of the intervention. Thus, as is usual practice in the department, physicians and department staff will be aware and educated on the QI initiative at the time of implementation. Default prescription order sets will be created in Aria (the radiation oncology electronic health record) for specific palliative treatment indications, namely brain/CNS, bone, soft tissue, and other palliative cases.

IGRT-LOCALIZATION INSTRUCTIONS:		
PRIMARY (Match for Treatment)	SECONDARY (EVAL)	
Modality: None	Modality: None	
Frequency: Other	Frequency: Other	
Match Instructions: Set up with attention to immobilization, tattoo markers, and weekly MV portal films	Additional / Special Instructions:	
Additional / Special Instructions: do not take KV-KV image		
Localization Instructions For CD Or Other If Different From Initial:		

Figure 1: Example of Default IGRT Prescription for Palliative Cases

Figure 2: Study Framework

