## 8.3 Coin-flip to select initial site (randomization)

Group 1 (PCAM physicians) and 2 (non-PCAM physicians) will be assigned to either the intervention or control group prior to study initiation by coin flip (rather than arbitrarily as has been done in past QI efforts). The control group will then rollover to the intervention arm after 2 months.

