## 9. Analysis plan

The primary analysis will use a mixed effects logistic regression model, where the unit of analysis is an individual patient, the outcome is use of daily x-ray imaging and the explanatory variables are time (pre-intervention vs. post-intervention period), dummy variable for whether the intervention is received, group (PCAM vs. satellite providers) and physician random effects. The coefficient of interest is the coefficient of whether the intervention is received. The physician random effects account for the clustering by physician. The study is analyzed at the physician level (patients clustered within physicians) rather than the practices site level because there are only two practice sites. Of the two practice sites – PCAM vs. non-PCAM sites – one group will be assigned to the intervention for the entire intervention period by coin flip, and the other group of providers will be assigned to the control for the first two months of the intervention. Randomly assigning the order of practice sites exposed to the intervention helps to blunt selection bias. For this analysis, we have 89% power to detect an effect of the intervention that reduces the probability of daily imaging by 0.2 for each physician.

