#### 2. Study arms

a. The intervention will consist of a default prescription order set that does not include daily imaging for palliative cases. Preceding the intervention, there will be a 12-month retrospective pre-intervention period that will establish baseline use of image guidance during palliative radiation at Penn. Implementation of the default will occur in an interrupted time series design with two comparison groups:

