#### Methods:

For the main analysis model, we used PROC GENMOD to fit models based on generalized estimating equations with a logit link and an independence correlation structure using the attending physician as the clustering unit with month and site as covariates. In sensitivity analyses, the main model was estimated by also adjusting for patient characteristics including age, sex, race,...,..,etc.

To obtain the adjusted difference in the percentage of patients receiving daily IGRT imaging between intervention and non-intervention groups and 95% confidence intervals (CIs), we used the bootstrap method, resampling patients 1000 times. Resampling of patients was by physician to maintain clustering at the physician level. All analyses were conducted in SAS version 9.4.

7

**Commented [SS7]:** CR: Note: It's possible we might use a different correlation structure. We can modify what goes in the list of the covariates for the sensitivity model.

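### One coin flip orders two groups, but the intervals count only physician-level variation, so a shift confined to PCAM or the satellites in the first period moves the intervention estimate without widening its error bars

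*Protocol*

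**What the plan says.** **Assignment.** Protocol 8.3 says the PCAM and non-PCAM physicians "will be assigned to either the intervention or control group prior to study initiation by coin flip", and Protocol 5.1 says the same ("These groups will be assigned to the intervention or usual care at the start of the study by coin flip"). There are two units and one flip. The group that starts as control crosses over later.

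**Protocol analysis.** Section 9 gives the number of sites as its reason for working at physician level: "analyzed at the physician level (patients clustered within physicians) rather than the practices site level because there are only two practice sites". Its model contains these terms: "time (pre-intervention vs. post-intervention period), dummy variable for whether the intervention is received, group (PCAM vs. satellite providers) and physician random effects". On dependence it says only "The physician random effects account for the clustering by physician". On randomisation it claims only that a random order reduces selection bias.

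**SAP analysis.** The Methods section fits a logistic GEE with "an independence correlation structure using the attending physician as the clustering unit with month and site as covariates". The interval for the adjusted difference comes from a bootstrap: "Resampling of patients was by physician to maintain clustering at the physician level". The primary model in SAP Adjusted Analysis (a) lists intervention, attending, location and time as separate terms. SAP section 2 describes the design differently: "Implementation of the default will occur in an interrupted time series design with two comparison groups".

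Neither document has a group-by-time term, a group-by-period variance component, or a stated assumption that PCAM and the satellites would have moved in parallel.

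**The concern.** Few randomised units is a limitation to declare. It does not license treating the physicians as the independent units, because all physicians in a group switch on the same date. If something else changes daily imaging at PCAM alone, or at the satellites alone, during the months when only one group has the default, every physician in that group moves together. The intervention coefficient absorbs the movement. The physician-level standard error does not, because it measures only how physicians differ from one another.

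At stake is the calibration of the main p-value and interval. A chance divergence between PCAM and the satellites could be reported as an effect of the default. The SAP's second primary outcome (section 4.a.ii) compares the two groups in exactly the period where such a divergence does most harm.

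**Working it through.** **Inputs from the documents**
- Protocol Table 2: 623 PCAM courses a year; satellites 56 + 39 + 55 + 52 = 202. Per month: 623/12 = 51.9 and 202/12 = 16.8.
- Baseline daily imaging: PCAM 81.4%; satellites (56×0.589 + 39×0.795 + 55×0.764 + 52×0.808)/202 = 148.0/202 = 73.3%.
- Periods: 12 baseline months, then 2 + 2 months (Protocol 5.2) or 3 + 3 months with roll-out months dropped (SAP).
- About 29 physicians (Protocol 5.3).

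**Assumed, not in the documents:** two-sided 5% alpha, a 20/9 physician split, a physician SD of 0.5–0.8 logits, and every group-by-time SD below.

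**1. The plan's own figure.** The 89% power for a 0.2 reduction cannot be reproduced, because alpha, the within-physician correlation, the physician split and the patient numbers are not stated. A plain two-proportion test of 79.3% against 59.3% in the first period gives 56% (2 months) or 76% (3 months). The present point does not depend on this. The 89% is used only to back out an implied standard error: 0.2/(1.960 + 1.227) = 0.0628.

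**2. How a one-group shift enters the estimate (linear approximation).**

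*SAP month model.* The estimate is the mean PCAM-minus-satellite difference over the 3 PCAM-only months, minus its mean over the other 12 + 3 = 15 months. A first-period shift loads +1 (PCAM) or −1 (satellites). A shift after crossover loads −3/15 = −0.2 (PCAM) or +0.2 (satellites). A PCAM shift lasting through both periods loads 1 − 0.2 = 0.8.

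*Protocol pre/post model.* There are two routes to the effect:
- Route A: PCAM post minus pre, less satellite first period minus pre.
- Route B: satellite post-crossover minus satellite first period.

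Both subtract the satellites' first period, so a shift there loads −1. Apart from that shared cell, the relative variances are:
- A: 1/(5×51.9) + 1/623 + 1/202 = 0.0104
- B: 1/(2×16.8) = 0.0297

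The five PCAM months include the crossover month. The weight on A is 0.0297/(0.0297 + 0.0104) = 0.74. A PCAM shift in either 2-month period loads 0.74×2/5 = 0.30. A satellite shift after crossover loads 1 − 0.74 = 0.26.

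**3. Effect on type I error, using the implied standard error.** Suppose independent shifts with SD s in the four post-baseline group-by-period cells. Then true SE = √(0.0628² + s²·Σload²), and actual alpha = 2[1 − Φ(1.96×0.0628/true SE)]. Σload² is 1 + 1 + 0.04 + 0.04 = 2.08 (SAP) and 1 + 0.296² + 0.296² + 0.259² = 1.24 (protocol).

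| Assumed s | SAP month model | Protocol model |
|---|---|---|
| 2 points | 7.5% | 6.5% |
| 3 points | 10.7% | 8.4% |
| 5 points | 19.8% | 14.3% |

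**4. Simulation of the SAP GEE.** Independence structure, month indicators, physician-clustered sandwich errors; 600–800 runs per cell. The comparator is a t-test on monthly PCAM-minus-satellite differences.

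| Assumed group shift | Physician-clustered GEE | Monthly-difference test |
|---|---|---|
| None | 8–9% | not reported |
| Monthly, SD 5 points | 12–13% | 4.5–6% |
| Monthly, SD 8 points | 20–21% | 4.5–6% |
| Whole step, SD 3 points | 14–15% | 7–10% |
| Whole step, SD 5 points | 25–28% | 15–19% |

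Monte Carlo error is at most about √(0.25×0.75/600) = 1.8 points for rates up to 25%. A separate run with step shifts on the logit scale gave 22% at SD 0.3, which is about 0.3×0.79×0.21 = 5 points.

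**5. Randomisation alone.** With two possible allocations, the smallest p-value is 1/2 one-sided and 1.0 two-sided. Any smaller p-value rests on modelling assumptions.

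**The case against.** **Much is already absorbed.** The group term removes stable differences between PCAM and the satellites, and the SAP's month covariate removes shifts common to both. A reader might infer that any group-specific shift is counted in full as intervention effect. The loadings do not support that: after crossover they are only about 0.2–0.3 in size, and a first-period PCAM shift loads about 0.30 in the protocol model.

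**The shift sizes are assumed.** Neither document gives monthly imaging rates by group, so nothing shows that shifts of 3, 5 or 8 points occur here. This stands. A single 5-point PCAM-only drop that loads fully would be significant only 13% of the time: Φ(0.05/0.0628 − 1.96) + Φ(−0.05/0.0628 − 1.96) = 0.125.

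**Part of the inflation has another cause.** With no shift the GEE already rejects 8–9% of the time, because there are few clusters. In one set of runs a small-sample factor with a t reference cut 9.1% to 6.2%. Measured from the no-shift rate, the rise due to group shifts is about 4 points (5-point monthly SD), 5–7 (3-point step SD) and 16–20 (5-point step SD).

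**The simulated model is the SAP's.** The protocol's mixed model and the SAP's bootstrap were not simulated. For the protocol model only the approximation in step 3 is available.

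**The satellites are four hospitals.** With independent hospital shifts, one set of runs fell from 25% to 22% (5-point step SD) and from 15% to 12% (5-point monthly SD). The problem shrinks but remains.

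**Partly disclosed.** The SAP calls the design an interrupted time series and plans monthly plots by cohort, and the protocol does not claim that the flip balances the groups. That is fair, but a plot does not enter the interval.

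**Conclusion.** The concern holds in a limited form. The section 9 rationale does not justify physician-level inference, and both plans leave group-by-time variation out of the error term. A shift in one group in the first period enters the estimate fully in the SAP month model and in the first-period contrast. In the protocol model it is −1 for the satellites and 0.30 for PCAM. In later periods it enters partly. In no case does the interval widen for it.

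Under the assumed SDs, the SAP GEE's type I error rises from 8–9% to 12–15% for modest shifts and to 25–28% for a 5-point step SD. These figures rest on the assumed shift sizes and physician split. They show sensitivity and do not estimate the error rate in this trial.

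A reader might also infer that the planned analysis is invalid and must be replaced by the monthly-difference test. The documents do not show that such shifts occur, and that test still rejects 15–19% of the time under 5-point step shifts. No two-group analysis can separate a shift lasting a whole step from the intervention. The plan needs an added analysis and an honest statement of what the interval assumes.

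**What to change.** 1. Keep the coin flip and the physician-clustered model. Add a small-sample correction to its standard error and use a t reference.
2. Beside it, pre-specify and report one analysis that counts group-by-month variation. This can be the monthly PCAM-minus-satellite difference, contrasting the 3 PCAM-only months with the 12 baseline and 3 both-exposed months on a t reference. Alternatively, add a group-by-month random effect to the model.
3. Base the conclusion on an effect that holds in both.
4. In Protocol section 9, replace the two-sites rationale with a statement of three things: the physician-level interval is conditional on no group-specific time shift; the causal strength is that of a controlled before-after series; and no two-group analysis can separate a shift lasting a whole step from the intervention.

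**Cost.** Wording and one extra model on data already planned for collection, and a wider interval. Simulated power for a 20-point effect was 71–72% for the GEE against 64% for the monthly-difference test, an apparent loss of about 7 points. That comparison is not size-matched. Calibrated to a true 5% size, the GEE gave 63% in one set of runs, so most of the gap reflects its inflated size.

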Overuse of IGRT is particularly apparent during palliative radiation treatments. Our department has demonstrated that for the palliative treatment of brain metastases standard, clinical immobilization and setup techniques without the use of daily IGRT are sufficient for treatment in routine cases. Moreover, evidence-based guidelines clearly state that "IGRT generally is not medically necessary in the palliative setting." Yet despite uncertain clinical need and decreasing reimbursements, physicians often reflexively order daily imaging for treatment.

4.3. Preliminary data. At our institution, across the University of Pennsylvania Health System (UPHS) Radiation Oncology network, 79% of palliative intent radiation courses over the past year (August 2015 – August 2016) utilized daily x-ray image guidance as part of the treatment paradigm. As shown in Table 1, despite clinical guidelines recommending against the use of daily IGRT in palliative cases, 83% of bone metastases, 82% of soft tissue metastases, and 57% of palliative brain/ CNS cases employed daily IGRT during the associated radiation treatment course.

Palliative Type	Total N	% Courses w Daily IGRT
Bone	459	83.4%
Brain/ CNS	133	57.1%
Soft Tissue	216	82.4%
Unknown	2	50.0%
SBRT	21	100.0%

Table 1: Use of Daily IGRT in Palliative Cases at UPHS by Treatment Indication

\*Daily IGRT defined as at least 80% (i.e., 4 of 5 days, on average) of treated fractions in a treatment course have IGRT

\*\*SBRT: Stereotactic Body Radiation Therapy

As shown in Table 2, the total number of palliative courses and associated daily IGRT varies across our main site and satellites. Our main site, the Perelman Center for Advanced Medicine (PCAM), has the highest volume of cases overall, and, hence, the highest number of palliative courses. All sites across the UPHS radiation oncology network, however, demonstrate high levels of daily IGRT usage in palliative courses. Over the past year, the number of palliative courses treated at each department was roughly stable over time as shown in Table 3, other than a slight rise in the number of cases treated during the month of June.

[figure not shown]
Location	Total N	% Courses w Daily IGRT
PCAM	623	81.4%
PAH	56	58.9%
СНН	39	79.5%
DH	55	76.4%
VF	52	80.8%
Unknown	6	66.7%
Grand Total	831	79.3%

**Table 2:** Use of Daily IGRT in Palliative Cases by UPHS Radiation Oncology Department

 Location

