## 5.2 Study duration

The duration of the study will be 27 months, including the 12 retrospective pre-intervention study period, 1 month for the intervention, 2 months for the first post-intervention study period, 1 month for the control to cross over to the intervention, and 2 additional months for observation in which all physicians are exposed. Analysis of data and dissemination of results will occur in the 9 month period following the  $2^{nd}$  post-intervention period.

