## 6. Subject recruitment

Not applicable. Subjects will include all UPHS radiation oncologists. As a result, no recruitment will be needed in this study.

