#### i. Intervention arm (Perelman Center for Advanced Medicine - PCAM)

- 1. 2/10/2017-3/9/2017: 1 month roll out
  - a. Intervention announced to entire group at faculty meeting and by email
  - b. Individual meetings with intervention group attendings to assure awareness and use of default prescription order
  - c. Educational meetings with therapists to introduce new default prescription
- 2. 3/10/2017-6/9/2017: 3 month intervention period
  - Only the intervention arm (PCAM) has access to the default option and the usual practice group (satellites) does not undergo the intervention
- 3. 6/10/2017-10/10/2017: Crossover period
  - a. Default intervention is introduced to usual care group.
- Intervention group continues to practice without any change.
- ii. Usual practice / control group (Pennsylvania Hospital, Chestnut Hill,

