#### Doylestown, Valley Forge)

- 1. 2/10/2017-6/9/2017: Control period
  - Usual practice group does not undergo intervention and serves as control to intervention group during this time
- 2. 6/10/2017-7/9/2017: 1 month roll out
  - a. Intervention announced to usual practice group at faculty meeting and by email
  - b. Individual meetings with usual care group attendings to assure awareness and use of default prescription order
  - c. Educational meetings with therapists to introduce new default prescription
- 3. 7/10/2017-10/10/2017: 3 month intervention period

a. Both arms undergo the intervention

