# 2. Unadjusted Analysis

- a. Daily IGRT
  - i. Calculate daily IGRT use during pre-intervention period (2/10/16-2/9/17)
    1. Display graphically by month and cohort (PCAM vs. satellites)
  - ii. Calculate daily IGRT use at PCAM and satellites after intervention implemented (2/10/17-10/10/17)
    - 1. Display graphically by month and cohort (PCAM vs. satellite)
    - 2. Indicate on graph when intervention occurred at PCAM (2/10/17) and satellites (6/10/17)
  - iii. Conduct statistical analysis of change in daily IGRT pre and post intervention with 95% CI and p values
    - 1. Change in daily IGRT use from baseline pre-intervention period to intervention periods in both the control and intervention arms
      - Intervention group: Pre-intervention period (2/10/16-2/9/17) use of daily IGRT vs. Post-intervention period (3/10-17-10/10/17) use of daily IGRT
      - Control group: Pre-intervention period (2/10/16-6/9/17) use of daily IGRT vs. Post-intervention period (7/10-17-10/10/17) use of daily IGRT
    - Change in daily IGRT use during first intervention period (3/10/17-6/9/17) between usual care group (control) and intervention arms

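### The unconditional 89% power does not hold for the protocol design with PCAM first, the order the SAP adopts, and it is not restated for the SAP's longer windows and new time term

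*Protocol*

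**What the plan says.** Protocol section 9 specifies a mixed effects logistic model with a pre/post time term, an intervention indicator, group (PCAM or satellites) and physician random effects. It then states: "we have 89% power to detect an effect of the intervention that reduces the probability of daily imaging by 0.2 for each physician". The sentence gives no alpha, sidedness, number of courses, physician variance or order of the groups. Baseline rates and volumes are in Table 2 (section 4.3), but the sentence does not refer to them.

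The order was to be set by coin flip (sections 5.1 and 8.3). After a 12-month baseline the protocol's calendar runs "1 month for the intervention, 2 months for the first post-intervention study period", then one crossover month and two further months. Section 8.3 agrees: "The control group will then rollover to the intervention arm after 2 months".

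The SAP (Study Overview, 2.a) has PCAM as the first group. The satellites are control from 2/10/2017 to 6/9/2017, which is four months: "Usual practice group does not undergo intervention and serves as control to intervention group during this time". Each group's own roll-out month is left out of the unadjusted comparisons (Analysis Plan, section 2). The Methods paragraph replaces the mixed model with a GEE that adjusts for month and site. It does not say how month is coded, and a comment in section 3 still asks whether time means days from intervention. The SAP has no power statement.

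**The concern.** Section 4.3 itself notes that "the total number of palliative courses and associated daily IGRT varies across our main site and satellites". In this design the scarce information is the unexposed time of the later group after the start. If PCAM starts, that control time comes from the satellites, at about 17 courses a month. If the satellites start, it comes from PCAM, at about 52 a month. One figure cannot describe both outcomes of the coin flip, and the sentence does not say that it is an average.

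This is the only power statement in either document, so a reader is likely to attach it to the analysis reported, which has a different order, calendar and time term from any that section 9 describes.

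**Working it through.** **Inputs.** Table 2: PCAM 623/12 = 51.92 courses a month at 81.4%; satellites 202/12 = 16.83 a month at (56×58.9 + 39×79.5 + 55×76.4 + 52×80.8)/202 = 73.3%. The reduction when exposed is 0.2, giving 61.4% and 53.3%. Assumed, because not stated: two-sided alpha 0.05.

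**The plan's own figure.** Model: group, pre/post time and intervention, fitted to expected cell counts. Satellites first, 2-month steps, roll-out months dropped, logistic Wald test: log odds ratio −0.9718, SE 0.3038, power = Φ(0.9718/0.3038 − 1.96) = 0.892. The stated 89% is reproduced.

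**The same calculation with PCAM first.** Log odds ratio −0.9688, SE 0.4359, power = Φ(0.9688/0.4359 − 1.96) = 0.604.

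**Why the orders differ.** On the linear scale the variance has a closed form. Write v = p(1−p)/n for each cell. Then

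Var = v(later group, unexposed post) + 1/[1/v(later group, exposed) + 1/S],

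where S = v(first group, exposed) + v(first group, pre) + v(later group, pre).

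| | PCAM first | Satellites first |
|---|---|---|
| Later group, unexposed post | 0.1958/33.67 = 0.00582 | 0.1514/103.83 = 0.00146 |
| Later group, exposed | 0.2489/33.67 = 0.00739 | 0.2370/103.83 = 0.00228 |
| S | 0.2370/207.67 + 0.1514/623 + 0.1958/202 = 0.00235 | 0.2489/67.33 + 0.1958/202 + 0.1514/623 = 0.00491 |
| Variance | 0.00760 | 0.00302 |
| SE | 0.0872 | 0.0549 |
| Power, Φ(0.2/SE − 1.96) | 0.631 | 0.954 |

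With PCAM first, about 34 unexposed satellite courses supply 0.00582/0.00760, or about three quarters, of the variance.

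**Roll-out handling.** The protocol does not say whether the first group's roll-out month counts as control time for the later group. If it does, unexposed satellite courses rise to 50.5 and PCAM-first power to 0.745 (logistic) or 0.767 (linear). Also keeping each group's own roll-out month, as exposed, gives 0.754 or 0.785. Satellites first becomes 0.955–0.981 and 0.974–0.993 respectively.

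**Physician clustering.** These are simulations of the protocol's mixed logistic model with 29 physicians, assumed splits between 15/14 and 24/5, and assumed physician SD of 0.3 to 1.5 on the logit scale. PCAM first gives 0.62–0.73 with roll-out months dropped and 0.76–0.82 with them counted. Satellites first gives 0.91–0.99.

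**SAP windows, PCAM first.** PCAM has 12 months before and 7 exposed; the satellites have 12 before, 4 unexposed and 3 exposed. For pre/post time on the linear scale, the unexposed satellite term is 0.1958/67.33 = 0.00291, the exposed one 0.2489/50.5 = 0.00493, and S = 0.2370/363.4 + 0.1514/623 + 0.1958/202 = 0.00186. The SE is 0.0653 and power is Φ(0.2/0.0653 − 1.96) = 0.865. Cell-level results, logistic/linear:

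| Time term | Own roll-out months dropped | Kept as exposed |
|---|---|---|
| Pre/post by calendar date | 84.1% / 86.5% | 84.8% / 87.7% |
| Month categories | 69.9% / 70.4% | 79.6% / 80.6% |
| Linear month | 98.0% / 99.2% | at least 99% |

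The mixed model with roll-out months dropped gives 87–92% for pre/post, 74% for month categories and 99% for linear month.

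With month categories, dropping PCAM's roll-out month leaves a month with satellite courses only, which says nothing about the intervention. Linear month gains its power by assuming a straight-line trend on the model scale.

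Pre/post must be defined by calendar date here. The unadjusted satellite comparison uses "Pre-intervention period (2/10/16-6/9/17) use of daily IGRT"; as a model term that definition would coincide with exposure, and the two could not be separated. Days from intervention was not calculated, because the SAP does not define it for unexposed courses.

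**Volume.** Table 1 includes 21 SBRT courses, so N is at most 831 − 21 = 810 before IMRT, proton and retreatment courses are removed. At 810, SAP-window power falls by about one point or less; the other exclusions cannot be counted from the documents.

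**The case against.** The figure was written before the coin flip, and several readings come close to it. Satellites first gives it directly. Averaging the two orders with roll-out time counted gives 85–89%. A one-sided 0.05 test with PCAM first and roll-out counted gives 84–89%. All of this stands. A reader might infer that the authors miscalculated, or that they assumed a particular order or a one-sided test. The documents support neither inference, because the inputs are not given.

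A reader might also conclude that the study as analysed has only 60–82% power. That does not follow either. The range belongs to the protocol's 2-month steps, which the SAP lengthened; with the SAP windows and a calendar pre/post term, power is back at 84–92%.

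Nor are baselines missing from the protocol, since Table 2 has them. Roll-out exclusion is stated only for the unadjusted analyses, not for the GEE, so both versions have to be shown for month categories.

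Finally, the SAP's comments are dated 10/15/17, after the last window closed on 10/10/17, and its Methods paragraph is in the past tense. A restated power changes nothing about conduct, and the planned 95% confidence intervals will show the precision achieved. That limits the weight of the point but does not make the unconditional sentence correct.

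**Conclusion.** The point holds as a minor one. Under the protocol's own model and calendar, 89% is attainable with satellites first (about 89–99%), but not with PCAM first at two-sided 0.05 (about 60–82%). In that order the reduction detectable at 89% power is about 0.28–0.30 with roll-out time dropped, or 0.23–0.25 with it counted, rather than 0.20. Under the SAP windows power runs from about 70% to about 99%, depending on a time coding and a roll-out rule that the SAP leaves open for its main model.

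The results rest on Table 2 rates and volumes and on assumed alpha, sidedness, physician SD and physician split. Using a common 79.3% baseline among the alternatives widens the PCAM-first range to about 53–84%. The SAP's GEE with bootstrap intervals is not what these figures describe. Severity is low because no sample size depends on the figure: "Subjects will include all UPHS radiation oncologists".

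**What to change.** Replace the 89% sentence with the power for a 0.2 reduction, or the reduction detectable at 89% power, for PCAM first under the SAP windows and the final main model. List with it:

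- two-sided alpha 0.05;
- planning rates of 81.4% (PCAM) and 73.3% (satellites), not observed results. If N excludes SBRT, recompute both rates without SBRT; Table 1 does not split those courses by site, so this needs the source data;
- the number of eligible courses a year after all section 5.6 exclusions;
- the between-physician SD on the logit scale;
- the time coding: month categories, linear month, or days from intervention with its definition;
- whether roll-out months enter the adjusted model.

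The last two belong in the SAP Methods paragraph whatever the power turns out to be. No single value should be filled in before they are settled. The 89% should not be attributed to either order unless the original calculation is on file.

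The cost is a few clauses and a short calculation, with no extra patients and no change to the windows. The downside is that the stated power may become less favourable.
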